2.1.1 General definitions

For information on general definitions, see the main SAP for the randomized part of the study except for the ones below.

Study day

For arm 1A, the reference start date for non-safety assessments is the date of start of study treatment.

Baseline

For arm 1A, for efficacy evaluations, the last non-missing assessment, including unscheduled assessments on or before the start of study treatment is taken as “baseline” value or “baseline” assessment. In the context of baseline definition, the efficacy evaluations also include performance status.

Extended follow-up

Additional summaries will be displayed to report deaths, all AEs, AEs related to study treatment, all serious adverse events (SAEs), SAEs related to study treatment and AESI collected up to 150 days after last administration of PDR001/LAG525.

2.2 Analysis sets

All below defined analysis sets will be used to analyze data from both the selection (Part 1) and expansion (Part 2) phases. Note, the immunogenicity (IG) analysis sets are outside the scope of the interim analyses (IA).

Full Analysis Set

The Full Analysis Set (FAS) comprises all subjects who received at least one dose of study treatment. This population will be the primary population for efficacy analysis.

Safety

The Safety Set is identical to the FAS.

Note: Even if the subject receives partial infusion of the treatment or only one component of the treatment, the subject will still be analyzed under PDR001+LAG525 treatment arm.

Biomarker analysis set

The biomarker analysis set, as it pertains to the secondary objective (Section 10.5.5 of the protocol), consists of all subjects in the safety set with an evaluable baseline tumor biopsy sample and at least one evaluable post-baseline tumor biopsy sample.

Evaluability for the analysis of the secondary objective will consist of the following:

- Having both tumor biopsy samples as stated above,
- Having quantifiable results for at least two assays to calculate the secondary endpoint as described in [Section 2.12.2](#).

Immunogenicity (IG) analysis sets

The immunogenicity prevalence set includes all subjects in the Full analysis set with a determinant baseline IG sample **or** at least one determinant post-baseline IG sample.

The immunogenicity incidence set includes all subjects in the Immunogenicity prevalence set with a determinant baseline IG sample **and** at least one determinant post-baseline IG sample.

See Section 2.10.1.1 of the main SAP for the randomized part of the study for the definition of determinant.

For more information on the additional analyses sets as well as subject classification and withdrawal of informed consent information, see the main SAP for the randomized part of the study.

2.2.1 Subgroup of interest

Subgroup analysis as described in the main SAP for the randomized part of the study may be only performed at the primary analysis (e.g. once all patients from part 2 have been enrolled and followed for at least 9 months) but not at interim analyses. Of note, LDH subgroup defined in the main SAP for the randomized part of the study as a stratification factor is not a stratification factor for this non-randomized section of the study. In addition, subgroup linked to ECOG performance status will be defined as 0 versus 1.

2.3 Subject disposition, demographics and other baseline characteristics

The Full Analysis Set (FAS) will be used for all baseline (including disease characteristics) and demographic summaries unless otherwise specified. Summaries will be reported for all subjects to assess baseline comparability. No inferential statistics will be provided.

Basic demographic and background data

All demographic and baseline disease characteristics data will be summarized and listed. Categorical data (e.g. gender, age groups: < 65 and ≥ 65 years, race, ethnicity, ECOG performance status, etc...) will be summarized by frequency counts and percentages; the number and percentage of subjects with missing data will be provided. Continuous data (e.g. age, weight, height, body mass index) will be summarized by descriptive statistics (N, mean, median, standard deviation, minimum and maximum). BMI (kg/m²) will be calculated as weight[kg] / (height[m]²) using weight at Screening.

Diagnosis and extent of cancer

Summary statistics will be tabulated for diagnosis and extent of cancer. This analysis will include the following: primary site of cancer at initial diagnosis, diagnosis of disease, BRAF mutation status, details of tumor histology/cytology, stage at study entry per AJCC Edition 8, time since initial diagnosis, time from initial diagnosis to first recurrence/progression (in months), time since most recent relapse/progression to randomization (in months), presence/absence of target and non-target lesions, sum of lesion diameter for target lesions at baseline, number and type of metastatic sites involved, and number of metastatic sites. Note: Presence/absence of target and non-target lesions will be based on the data collected on RECIST target/non-target lesion assessment eCRF pages. Metastatic sites will be based on diagnosis page. Tumor (T) stage at study entry, lymph nodes (N) stage at study entry, and metastases (M) at study entry will be further listed in the Subject disease history listing.

Medical history

Medical history and ongoing conditions will be presented identically to the content in the main SAP for the randomized part of the study.

2.3.1 Subject disposition

The number (%) of enrolled Arm 1A subjects included in the FAS will be presented overall. The number (%) of screened and not-treated subjects and the reasons for screening failure will also be displayed. The number (%) of subjects in the FAS who are still on treatment, who discontinued the study phases and the reason for discontinuation will be presented.

The remaining summaries for subject disposition are identical to those in the main SAP for the randomized part of the study.

The following summaries will be provided (with % based on the total number of FAS patients):

- Number (%) of patients who completed the screening phase but not treated,
- Primary reason for not being treated,
- Number (%) of patients who were treated,
- Number (%) of patients who are still on-treatment,
- Number (%) of patients who discontinued the study treatment phase,
- Primary reason for study treatment phase discontinuation,
- Number (%) of patients who have entered the post-treatment follow-up,
- Number (%) of patients who have discontinued from the post-treatment follow-up,
- Reasons for discontinuation from the post-treatment follow-up,
- Number (%) of patients who have entered the survival follow-up.

Protocol deviations

Summaries and listing for protocol deviations are identical to those in the main SAP for the randomized part of the study.

Analysis sets

The number (%) of subjects in each analysis set (defined in [Section 2.2](#)) will be summarized.

2.4 Treatments (study treatment, rescue medication, concomitant therapies, compliance)

The Safety set will be used for the analyses below. Categorical data will be summarized as frequencies and percentages. For continuous data, mean, standard deviation, median, 25th and 75th percentiles, minimum, and maximum will be presented.

2.4.1 Study treatment / compliance

Study treatment and compliance information will be presented identically for the IAs, the primary analysis and the final analysis. Therefore, more details on study treatment and compliance information can be found in the main SAP for the randomized part of the study.

For PDR001 and LAG525, for the calculation of the dose intensity, planned dose intensity and relative dose intensity, the full theoretical treatment cycle duration (e.g. 28 days) for the last cycle will be considered : the modified duration of exposure will use the last date of exposure of study drug as defined in the main SAP for the randomized part of the study, but without cutting at the date of death, last contact date or cut-off date in case the patient died, was lost to follow-up, before the end of the cycle or the last exposure date is going beyond the cut-off date, respectively. [Table 2-1](#) below reflects the definition of the last date of exposure of study drug to be used for the modified duration of exposure in the dose intensity calculation.

Duration of exposure to study treatment, dose intensity and planned dose intensity

Duration of exposure to study treatment (days) = (last date of exposure to study treatment) – (date of first administration of study treatment) + 1.

The last date of exposure to study treatment is the latest of the last dates of exposure to PDR001 and to LAG525 (see [Table 2-1](#) below).

Table 2-1 Definition of last date of exposure of study drug

Scenario	Definition of last date of exposure of study drug	Example
PDR001 LAG525	
The planned end date of the last cycle in which the last non-zero dose of the investigational drug was last administered (i.e last date of administration + (planned interval duration-1day))
 
The note below will not be applicable for dose intensity calculation : Note : If the patient died or was lost to follow-up before the derived last date, the last date of exposure to investigational drug is the date of death or the date of last contact, respectively
	
Example 1: If PDR001 or LAG525, is administered every four weeks, the last date of exposure is the date of administration in the last cycle + 27 days.

	If the derived last date of exposure goes beyond the data cutoff date, it should be truncated to the date of data cutoff.	
--	---	--

Dose intensity and planned dose intensity

For drugs administered every 4 weeks (PDR001 and LAG525), the dose intensity and planned dose intensity will be reported in mg/cycle, defined as follows :

- $DI \text{ (mg / cycle)} = (\text{Actual Cumulative dose (mg)} / \text{modified duration of exposure to study treatment (days)}) * 28$, where modified duration of exposure (days) = last date of exposure of study drug (as defined in [Table 2-1](#) above) - (date of first administration of study drug) + 1.

If for example, the duration of exposure to PDR001 is 6 days because patient died 6 days after first day of dosing, the modified duration of exposure to PDR001 used in dose intensity calculation will be 28 days.

- PDI (mg/cycle) is 400 mg/cycle and 600 mg/cycle, for PDR001 and LAG525, respectively.

Dose interruptions or permanent discontinuations

The number of subjects who have dose permanent discontinuations, dose interruptions, and the reasons, will be summarized separately for each study drug, as described in the main SAP for the randomized part of the study.

Treatment beyond RECIST progression

The number of subjects who continue treatment beyond RECIST1.1 progression according to local investigators assessment based on protocol specified criteria will be summarized. It includes all subjects who received any study treatment (i.e. at least one dose of any component of the study treatment) after RECIST 1.1 progression assessed by local investigators. Those subjects will be identified using the field “Will the subject continue treatment beyond disease progression as per RECIST1.1?” on the Verification for Treatment beyond RECIST1.1 PD CRF pages.

2.4.2 Prior, concomitant and post therapies

Prior anti-cancer therapy

The number and percentage of subjects who received any prior anti-neoplastic medications, prior checkpoint inhibitor therapy, prior anti-neoplastic radiotherapy, prior anti-neoplastic surgery, or other therapies not defined by the previous categories, will be summarized. Prior anti-neoplastic medications will be summarized by therapy type (e.g. chemotherapy, hormonal therapy, immunotherapy etc.) and by setting (e.g. adjuvant, metastatic, etc.). Summaries will include total number of regimens, time from last treatment to progression for the last therapy, type of therapy received at any time or as last systemic therapy for unresectable and metastatic melanoma prior to enrollment (checkpoint inhibitor vs targeted therapy vs Other) excluding

radiotherapy and surgery, best response to last systemic therapy, to anti Anti-PD-1/Anti-PD-L1 therapy and best response to any immunotherapy, based on RECIST v1.1.

For radiotherapy, time since last radiotherapy, locations and setting of last therapy will be summarized. For prior surgery, time since last surgery and procedure will be summarized.

The prior checkpoint inhibitor therapy will be further summarized by type of checkpoint inhibitor therapy (Anti-PD-1, Anti-CTLA-4, and combination therapy of anti-CTLA-4 and anti-PD-1). The prior targeted therapy will be further summarized by type of targeted therapy (BRAF Inhibitor and MEK Inhibitor). The medication therapy type of any combination therapy will be classified based on the types of treatment taken at each regimen. For example, a combination therapy of targeted therapy and immunotherapy will be classified in both categories with appropriate sub-types.

Swimmer plot will be performed to present the subject's response according treatment duration. The different type of checkpoint inhibitor therapy (Anti-PD-1, Anti-CTLA-4, and combination therapy of anti-CTLA-4 and anti-PD-1, ...) received by the patient will be presented in parallel on the same graph, with the duration of the different prior therapy and best response to prior therapy. This plot will be produced at time of interim analyses, if number of patients is appropriate to keep the plot readable, for patients who responded (BOR in (CR,PR)) or with a BOR as SD.

Separate listings will be produced for prior anti-neoplastic medications, radiotherapy, and surgery.

Anti-neoplastic medications will be coded using the World Health Organization (WHO) Drug Dictionary (WHO-DD); anti-neoplastic surgery will be coded using MedDRA. Details regarding MedDRA and WHO-DD version will be included in the footnote in the tables/listings.

The above analyses will be performed using the FAS.

Post treatment anti-cancer therapy

Anti-neoplastic therapies since discontinuation of study treatment will be listed and summarized by ATC class, preferred term, by means of frequency count and percentages using FAS at primary and final analysis. The number and percentage of patients who reported at least one anti-neoplastic therapy since discontinuation of study treatment by category (see main SAP for the randomized part of the study Table 2-7) will be reported.

Concomitant medications

Summaries and listings as described in the main SAP for the randomized part of the study will be provided at primary and final analysis.

2.5 Analysis of the primary objective

The primary objective is to demonstrate the antitumor activity of spartalizumab in combination with LAG525 as measured by overall response rate (ORR) in previously treated unresectable or metastatic melanoma LAG-3 positive subjects. In particular, for the IAs, the primary objective will be to determine if investigator assessed ORR is sufficient to allow for the non-randomized arm 1A to be expanded or not.

2.5.1 Primary endpoint

Confirmed ORR is defined as the proportion of subjects with confirmed best overall response (BOR) of complete response (CR) or partial response (PR) according to RECIST 1.1.

Of note, BOR of SD will be assigned if at least one SD assessment (or better) occurred > 11 weeks after randomization (and not qualifying for CR or PR).

Tumor assessments performed after the start of any further antineoplastic therapy (i.e. any additional secondary antineoplastic therapy, radiotherapy or surgery, including limited-field palliative radiotherapy) will not be considered in the assessment of BOR. Further antineoplastic therapies will be identified via protocol deviations and from the data collected on “antineoplastic therapies since discontinuation of study treatment” (e)CRF pages. Of note, “biopsy” will not be considered as a new antineoplastic surgery.

For additional information on the primary endpoint, see the main SAP for the randomized part of the study.

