Table 2-7	Categories of anti-neoplastic therapies since discontinuation
Category	Sub-category
Immunotherapy	Anti-CTLA-4
	Anti-PD-1/Anti-PD-L1
	Combination Anti-CTLA-4 + Anti-PD-1/Anti-PD-L1
	IL-2
	Interferon
	Other or investigational
Targeted therapy	
Chemotherapy	
Radiotherapy	
Surgery	
Other or investigational	

Concomitant medications

Concomitant therapy is defined as all interventions (therapeutic treatments and procedures) other than the study treatment administered to a patient coinciding with the study treatment period. Concomitant therapy include medications (other than study drugs) starting on or after the start date of study treatment or medications starting prior to the start date of study treatment and continuing after the start date of study treatment.

Concomitant medications will be coded using the World Health Organization (WHO) Drug Reference Listing (DRL) dictionary that employs the WHO Anatomical Therapeutic Chemical (ATC) classification system and summarized by lowest ATC class and preferred term using

frequency counts and percentages. Surgical and medical procedures will be coded using MedDRA and summarized by SOC and preferred term. Concomitant medications with immunosuppressive intent will be summarized by lowest ATC class and preferred term using frequency counts and percentages.

All reported systemic steroids will be summarized by lowest ATC class and preferred term using frequency counts and percentages. Reported cumulative dose and maximum cumulative dose, adjusted for relative anti-inflammatory potency [Schimmer and Parker 1996], will also be summarized along with route of administration.

Table 2-8 Systemic steroid anti-inflammatory potency relative to Hydrocortisone

Steroid Name	Anti-inflammatory potency, relative to Hydrocortisone
Hydrocortisone	1
Cortisone acetate	0.8
Prednisone	4
Prednisolone	4
Methylprednisolone	5
Dexamethasone	30

All summaries will include:

1. Medications starting on or after the start of study treatment but no later than 30 days after last dose of study treatment and
2. Medications starting prior to start of study treatment and continuing after the start of study treatment.

Additional summaries will be provided to report medications starting between 31 days after last dose of study treatment and 150 days after last dose of PDR001.

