2.5.1 Primary endpoint

Confirmed ORR is defined as the proportion of patients with confirmed best overall response (BOR) of complete response (CR) or partial response (PR) according to RECIST 1.1 (see Appendix 2 of the protocol). For the primary analysis, ORR will be calculated based on the FAS using local investigators review of tumor assessment data. ORR will be summarized using descriptive statistics (N,%) along with 2-sided exact 95% confidence interval (CI) [Clopper and Pearson 1934]. Tumor assessments performed before the start of any further antineoplastic therapy (i.e. any additional secondary antineoplastic therapy or surgery) will be considered in the assessment of BOR. Limited-field palliative radiotherapy may be allowed after documented discussion with Novartis (see Section 6.4.4 of the protocol). For patients who receive limited-field palliative therapy, this therapy should not be considered in determining anti-neoplastic therapy usage.

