2.6.1 Key secondary endpoint

For information on the key secondary endpoint, see the main SAP for the randomized part of the study. Note, due to small sample size at 1st interim analysis, only listings will be generated for DoR.

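### Arm 1A bars scans after palliative radiotherapy from best overall response, but its two named data sources would ordinarily miss sponsor-agreed radiotherapy given during study treatment

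*SAP*

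**What the plan says.** The SAP file holds two plans: the main SAP for the randomized arms and a separate SAP for the non-randomized Arm 1A.

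- **Main SAP, 2.5.1.** "Limited-field palliative radiotherapy may be allowed after documented discussion with Novartis", with a pointer to protocol Section 6.4.4. The analysis rule follows: "For patients who receive limited-field palliative therapy, this therapy should not be considered in determining anti-neoplastic therapy usage". Scans after such radiotherapy therefore stay in the derivation of best overall response (BOR).
- **Arm 1A SAP, 2.5.1, rule.** Scans after any further antineoplastic therapy, "radiotherapy or surgery, including limited-field palliative radiotherapy) will not be considered in the assessment of BOR".
- **Arm 1A SAP, 2.5.1, sources.** "Further antineoplastic therapies will be identified via protocol deviations and from the data collected on" the eCRF pages titled "antineoplastic therapies since discontinuation of study treatment". No other source is named. The section ends by sending the reader to the main SAP for more on the endpoint, with no exception for the radiotherapy sentence.
- **Arm 1A SAP, 2.6.1.** "For information on the key secondary endpoint, see the main SAP for the randomized part of the study". Sections 2.6.3 and 2.7.3 take the DoR, PFS and OS censoring rules from the main SAP in the same way.

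**The concern.** The Arm 1A rule is clear, but the derivation it prescribes does not reach every patient the rule covers. The patient most affected is one who is still on treatment, has a first partial response, receives agreed palliative radiotherapy and then has a confirming scan. The definition makes that scan unusable. A program written from the two named sources would not see the radiotherapy and would count the response.

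Two loose ends add to this. The closing reference to the main SAP does not set aside that plan's opposite sentence. The DoR and PFS rules that Arm 1A borrows censor at new anticancer therapy, but those sections do not say whether limited-field palliative radiotherapy is such therapy.

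The primary endpoint is confirmed ORR by local assessment in an open-label arm, with three decision points on the responder count. Who counts as a responder should not depend on a programming choice made after the data are seen.

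**Working it through.** **1. Which radiotherapy do the named sources find?**

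| Palliative radiotherapy in Arm 1A | Deviations | Post-discontinuation pages | Exclusion applied? |
|---|---|---|---|
| After study treatment has ended | not needed | yes | yes |
| During treatment, in breach of the protocol | yes | no | yes |
| During treatment, agreed with the sponsor | ordinarily no | no | **no** |

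Row 1: Arm 1A 2.4.2 reports "The number and percentage of patients who reported at least one anti-neoplastic therapy since discontinuation of study treatment by category", using Table 2-7 of the main SAP, and that table has a category "Radiotherapy". Row 3 rests on main SAP 2.5.1, which says the radiotherapy may be allowed after discussion. That allowed use is not logged as a deviation is an inference, because protocol Section 6.4.4 was not at hand.

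**2. Example patient:** partial response, agreed radiotherapy on treatment, partial response at the next scan.

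- Arm 1A definition: the second scan is unusable, so the response is unconfirmed and the patient is a non-responder.
- Arm 1A as programmed from its named sources: responder.
- Main SAP rule: responder.

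**3. The plan's own boundaries, reproduced first** (Arm 1A 2.5.2).

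Primary test: reject if the exact 95% lower limit exceeds 15%. For x responders in n, the lower limit is the 0.025 quantile of Beta(x, n−x+1), and the upper limit is the 0.975 quantile of Beta(x+1, n−x). For 23/100 this gives 15.17% to 32.49%, matching the stated (15.2, 32.5).

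Interim rule: P(ORR ≥ 20%) > 70% with a Beta(1,1) prior, so P = 1 − F(0.20), where F is the distribution function of Beta(y+1, n−y+1). The stated boundaries are 5/20 and 9/40, and both reproduce.

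**4. Effect of removing responders.** The number affected is not in the document; 0 to 2 is assumed.

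| Decision | At boundary | One fewer | Two fewer |
|---|---|---|---|
| Interim 1, n=20 | 5: 0.769, met | 4: 0.586, futile | 3: 0.370, futile |
| Interim 2, n=40 | 9: 0.704, met | 8: 0.562, futile | 7: 0.407, futile |
| Primary, n=100 | 23: 15.2%, reject | 22: 14.3%, not rejected | 21: 13.5%, not rejected |

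One affected responder matters only if the programmed count is exactly at the boundary. Two matter at the boundary or one above it: 24/100 has a lower limit of 16.0%, and 24 − 2 = 22 gives 14.3%. Further above the boundary, the decision stands and only the estimate moves, by 1 percentage point per responder at n=100.

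**The case against.** The strongest reply is that these are two plans for two sections of the study. The main SAP is written to protocol version 01 and the Arm 1A SAP to amendment 05. The Arm 1A plan states its own explicit rule and cites the main SAP only for further information. On the natural reading its sentence governs Arm 1A. **This stands**, and a reader who infers that Arm 1A adopts the opposite rule goes too far. What remains is that 2.5.1 writes no precedence, although the same plan marks overrides elsewhere (2.1.1, 2.8.1, 2.8.2).

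Other stronger readings are also not supported:

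- *That palliative radiotherapy is missing from Arm 1A's sources altogether.* Only agreed, on-treatment use is missed.
- *That DoR and PFS in Arm 1A follow the opposite rule.* The main SAP's radiotherapy sentence stands in its ORR section. Its DoR and PFS sections are silent, so this is a missing definition.
- *That shrinkage of an irradiated target lesion is credited to the drug.* The SAP says nothing here about which lesions may be irradiated; the protocol section and response appendix it cites were not at hand.
- *That scoring the randomized arm and Arm 1A differently spoils a comparison.* Arm 1A was added after encouraging arm 1 results, but it is tested on its own against 15%, and no formal ORR comparison with the randomized arm is planned.

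It is also fair to say that one responder changes the result at any cut-off. The figures show how the decisions respond, not how likely a reversal is.

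**Conclusion.** The point holds as a mismatch between a stated exclusion and the data used to carry it out. As written, Arm 1A would ordinarily fail to exclude scans after sponsor-agreed palliative radiotherapy given during study treatment, and confirmed ORR could include responses that its definition rejects.

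The size cannot be estimated because the document gives no radiotherapy frequency. Under the assumed 0 to 2 affected responders, the effect ranges from nothing to a reversed decision, and reversal needs a count at or just above a boundary. At the interims, meeting the threshold only leads the sponsor to consider expansion. The conclusion rests on the inference that agreed radiotherapy is not recorded as a deviation; if it is, the gap closes. No view is taken on whether the radiotherapy should be permitted.

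**What to change.** 1. In Arm 1A 2.5.1, add the on-treatment concomitant procedure and radiotherapy records to the sources for further antineoplastic therapy. Main SAP 2.4.2 already codes concomitant procedures, and Arm 1A 2.4.2 adopts those summaries. Confirm which page records on-treatment radiotherapy. Apply the source at both interim looks too, since the concomitant tables are planned only for the primary and final analyses.
2. State that the Arm 1A rule replaces the palliative-radiotherapy sentence of main SAP 2.5.1 for Arm 1A.
3. Use the same definition of new anticancer therapy for DoR and PFS censoring in Arm 1A.
4. Report Arm 1A ORR under the main SAP's rule as a sensitivity analysis.

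Cost: a few sentences, one more data source in the derivation and one extra ORR table. A few responses may be lost, so ORR could be slightly lower. No stated boundary changes.
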